3.2. Study Population

3.2.1. Selection of Study Population

Subjects within the initial trial subset of 18 subjects (Stage 1 and 2) and in the AITL expansion cohort who do not receive at least one dose of tipifarnib will be replaced. Subjects within the initial trial subset of 18 subjects (Stage 1 and 2) and in the AITL expansion cohort who are unable to provide archival tumor tissue by the end of Cycle 1 and who did not have a biopsy performed prior to initiation of tipifarnib treatment will be replaced. Replacement subjects will have available tumor tissue identified at the time of screening. In addition, subjects with archival tissue that is of insufficient quality for biomarker evaluation, may be replaced.

3.2.2. Removal of Subjects from Treatment or Assessment

Subjects may withdraw their consent to participate in this study at any time without prejudice. The Investigator must withdraw from the study any subject who requests to be withdrawn. A subject's participation in the study may also be discontinued at any time at the discretion of the Investigator and in accordance with his/her clinical judgment. Every effort should be made to complete, whenever possible, the tests and evaluations listed for the End of Treatment visit. More details are available in Protocol Section 8.4.

3.3. Premature Discontinuation of the Trial

This trial may be discontinued prematurely in the event of any of the reasons listed in Protocol Section 8.5.

3.4. Definition of End of Study

For administrative and safety reporting purposes, the end of this clinical study is defined as 12 months from enrollment of the last enrolled study subject. If the last enrolled study subject discontinues treatment within 12 months of study enrollment, the End of Study will occur no earlier than the date of the last enrolled subject's safety follow-up assessment performed approximately 30 days after treatment discontinuation (or until initiation of another anti-cancer therapy). At the time of End of Study, provisions will be made to transition all remaining study

subjects who demonstrate sustained clinical benefit beyond the end of the study to other means of continued treatment with appropriate safety monitoring, e.g., single patient treatment protocol.

3.5. Randomization and Blinding

This is a single arm open label study. There is no randomization or blinding involved in this study.

[figure not shown]
4. SAMPLE SIZE CONSIDERATIONS

The study can enroll up to 70 participants. A multi-stage study design, which potentially assumes enrollment of the patients in three consecutive groups (11, 7, and up to 52 participants) will be employed. This design is intended to allow for the termination of accrual in case of unacceptably low efficacy. The objective responses will be evaluated in the first 11 participants (Stage 1) assessed in a Full Analysis Set (FAS). If 0-1 objective responses are observed after the first 11 evaluable subjects, the study will be closed to further enrollment. If 2-4 responses are observed, 7 additional subjects will be enrolled (Stage 2). Treatment will be considered of further interest (successfully passing Stage 2 to full enrollment) if at least 4 responses are observed (out of 18 subjects) in Stage 2.

In order to assess the operating characteristics of the design the following assumptions are made:

- Null hypothesis of ORR = 10% is tested using a two-sided binomial test (based normal approximation) with significance level $\alpha \leq 0.05$.
- All participants, despite population heterogeneity in terms of sub-types, have the same true ORR.
- Study total sample size is 65 evaluable participants given successful transition from stages 1 and 2 to full enrollment.

[figure not shown]
[Figure 1](#) depicts the relationship between the true ORR and power (red line) – probability of rejecting the null hypothesis given the assumptions above. It also shows the likelihood of passing Stage 1 (blue line) and Stage 2 (green line). When the true ORR is 30%, the probability of passing Stage 2 and rejecting the null hypothesis at the end of the study ($N = 65$) is approximately 80%. These probabilities are increasing to approximately 99% when the true ORR is 50%. For ORR = 10%, the probability of passing Stage 1 is 30% (and 8% to pass Stage 2).

Figure 1: Operating Characteristics of Study Design

Further sample size considerations are related to assessment of ORR in the subgroup of participants with AITL (N = 12) and CXCL12 (N = 12) subtypes. Figure 2 visualizes a 95% two-sided confidence interval for a hypothetical observed number of responders in the cohort consisting of 12 participants. It should be noted that the method of evaluating the confidence interval changes from Wilson¹ to Pearson-Clopper² if the number of responders falls below three.

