6 OBJECTIVES

6.1 Primary Objectives and Endpoints

Primary Objective: To determine the antitumor activity in terms of objective response rate (ORR) of tipifarnib in subjects with relapsed or refractory peripheral T-cell lymphoma (PTCL).

Primary endpoint: Response assessments according to the Lugano Classification and/or mSWAT.

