8. EFFICACY ANALYSIS

8.1. Primary Efficacy Analysis

The primary endpoint will be based on response assessments according to the Lugano Classification (Protocol Appendix II). Either complete or partial responses can contribute to an objective response. The objective response rate, \hat{p}_{ORR} , will be estimated as a ratio of subjects with an objective response to the number of subjects (N) in the FAS data set.

The 95% Confidence Interval for ORR will be calculated using Wilson³ approximation.

If $\hat{P}_{ORR} \times N \leq 4$, the exact Clopper-Pearson⁴ method will be used for interval estimation.

Null hypothesis $H_0: \hat{P}_{ORR} = 10\%$ versus $H_A: \hat{P}_{ORR} > 10\%$ will be tested at $\alpha = 0.05$ significance level using a two-sided binomial test. The choice of test statistics will be driven by the method used for interval estimation.

The ORR analysis will be presented by means of a summary table and visualization. A summary table of the objective response rates will be provided for the primary efficacy endpoint for both the FAS [REDACTED] populations. [REDACTED]

The ORR will also be analyzed by study population subgroups (part of the secondary analysis) which are based on the genetic sub-types.

Sensitivity analysis, as part of the exploratory analysis, may also include analysis using different statistical approaches (different methods for interval estimation variants of normal approximation, Agresti-Coull, Pearson-Clopper, etc.), one-sided confidence intervals, test statistics, or a modelling framework). Exploratory analyses may also include a logistic regression modeling framework to evaluate the effect of genetic sub-types and other covariates on ORR.

Additional sensitivity and subgroup analysis, as part of exploratory analysis, may be conducted as deemed appropriate.

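### SAP 8.1 moves the formal test of ORR = 10% from the first 18 unselected subjects to the pooled, AITL-enriched FAS, and SAP 14 does not declare the move

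*SAP*

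**What the plan says.** **Protocol.** The Synopsis (Statistical Methods) and Sections 8.1 and 12.4 tie the 10% versus 30% hypothesis to a two-stage design in the first 18 subjects, with no selection by histology or genotype. Eleven subjects are treated first and enrolment closes on 0 or 1 response. The drug is of further interest at 4 or more responses in 18. The stated level is one-sided 0.087 with 80% power. The AITL and CXCL12+ cohorts (12 each) carry only probability statements about the true rate. Section 12.4 and SAP Section 3.1 both say that no hypothesis is tested for the 20-subject AITL/TFH extension. Section 12.2.1 plans ORR estimates by histology with exact intervals, and no pooled test.

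**SAP.** Section 4 presents 11, 7 and up to 52 subjects as three groups of one design, the last reached by "successfully passing Stage 2 to full enrollment". Its operating characteristics rest on the listed assumptions "Null hypothesis of ORR = 10% is tested using a two-sided binomial test (based normal approximation") and "All participants, despite population heterogeneity in terms of sub-types, have the same true ORR", with 65 evaluable subjects. Section 8.1 estimates ORR "as a ratio of subjects with an objective response to the number of subjects (N) in the FAS data set" and tests 10% at the 0.05 "significance level using a two-sided binomial test", while writing the alternative as greater than 10%. Section 14 lists the move to pooled estimation. It does not mention the test.

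**The concern.** The tested population, its size, the alpha and the sidedness all differ from the protocol, and the SAP's own list of changes names none of them. This matters because the added subjects were not a continuation of the unselected cohort. Protocol Sections 8.1 and 12.4 say that the AITL cohort followed responses in both early AITL subjects, that the CXCL12+ cohort followed better outcomes in CXCL12-high subjects, and that the extension followed high activity in AITL. The common-ORR assumption therefore conflicts with the reasons given for enrolling most of the sample.

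A primary p-value below 0.05 would be read as activity in relapsed or refractory PTCL generally. In this mixture it could come from AITL alone, and the SAP gives no caution to that effect. It is also unclear whether the extension subjects, said to be outside any hypothesis test, enter this one.

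**Working it through.** **1. Protocol design.** Write b(x; n, p) for the binomial probability.
- P(stop at stage 1) = b(0; 11, p) + b(1; 11, p) = 0.697 at 10% and 0.113 at 30%, as stated.
- P(success) = sum over x from 2 to 11 of b(x; 11, p) × P(Bin(7, p) ≥ 4 − x) = 0.0875 at 10% and 0.800 at 30%. The protocol states 0.087 and 80%.

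**2. SAP design.** For more than 4 responders SAP 8.1 uses the Wilson interval, whose matching test is the score test: reject when z = (k − 0.1N)/√(0.09N) > 1.96.
- N = 65: k = 11 gives 4.5/2.419 = 1.86 and k = 12 gives 5.5/2.419 = 2.27, so the cutoff is 12.
- P(at least 2 of 11, at least 4 of 18, and at least 12 of 65) = 0.797 at ORR 30% and 0.992 at 50%. The SAP states about 80% and 99%.
- At 30%, passing the 4/18 gate alone has probability 0.800, so nearly all of the planned power is the gate.
- At a common ORR of 10% the whole procedure rejects with probability 0.012, against 0.087 in the protocol. Under its own assumption the SAP procedure is the stricter one.

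**3. Dropping the common ORR.**
- Protocol Section 5.2 reports 50 subjects enrolled, 23 of them AITL (17 evaluable). That leaves 50 − 23 = 27 others.
- Assumptions: all 27 others are evaluable, and all 20 extension subjects are enrolled and evaluable. AITL/TFH = 17 + 20 = 37, and N = 37 + 27 = 64.
- Cutoff at N = 64: k = 11 gives 4.6/2.4 = 1.92 and k = 12 gives 5.6/2.4 = 2.33, so again 12.
- P(reject) = P(Bin(37, pA) + Bin(27, 0.10) ≥ 12), stage gates ignored:

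| AITL/TFH ORR (pA) | Expected responses | P(reject) |
|---|---|---|
| 10% | 3.7 + 2.7 = 6.4 | 0.024 |
| 30% | 11.1 + 2.7 = 13.8 | 0.76 |
| 40% | 14.8 + 2.7 = 17.5 | 0.97 |
| 50% | 18.5 + 2.7 = 21.2 | >0.99 |

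If only 24 of the 64 have the higher rate (for example, 7 of the 20 extension subjects), P(Bin(24, pA) + Bin(40, 0.10) ≥ 12) is 0.45, 0.75 and 0.93 at 30%, 40% and 50%. For reference, Section 5.2 gives an AITL ORR of 52.9% (9 of 17).

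**4. With the 4/18 gate.** Place 2 AITL subjects at random among the first 18, as the protocol reports, with 37 AITL/TFH in all and N = 65. P(gate passed) is 0.149, 0.183 and 0.220 at AITL ORR 30%, 40% and 50%. P(gate passed and pooled test rejects) is 0.141, 0.182 and 0.219. The ratios are 0.141/0.149 = 0.95, 0.182/0.183 = 0.99 and 0.219/0.220 = 0.99 or higher. The gate rarely passes when the other subjects are at 10%, but once it has passed, the pooled test adds almost no further check.

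**The case against.** The primary objective covers all relapsed or refractory PTCL, the protocol makes the FAS the primary efficacy population, and Protocol Section 12 leaves the detail of the primary analysis to the SAP. Pooled estimation is therefore legitimate, and it is declared. The common ORR is labelled as a planning assumption. Subtype ORRs with intervals are already planned as secondary analyses, and SAP Section 12 describes data by cohort. All of this stands. It answers the estimate, not the undeclared test.

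The illustration is also only that. Holding every other subject at 10% does not describe the reported data: the non-AITL CXCL12+ responses number 5 − 2 = 3, in about 12 − 4 = 8 evaluable subjects. It shows what a rejection can mean, not what it will mean.

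The absence of a hypothesis test in the extension may mean only that no separate test is done there. That reading is natural, but the SAP should then say that these subjects enter the pooled test.

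Stronger inferences are not supported:
- **Alpha inflation.** A reader might infer it from the larger sample and added cohorts. Under a common 10% ORR the error rate is 0.012, below the protocol's 0.087.
- **A result that turns on the test version.** "The choice of test statistics will be driven by the method used for interval estimation", and above 4 responders that points to the score test. The score, Wald and exact versions disagree only at about 12 or 13 responses. A passed 4/18 gate, with only 2 early AITL responders, implies at least 2 non-AITL responders in the first 18. Added to the 9 AITL and 3 non-AITL CXCL12+ responses reported, that is at least 14, if all of them count under the SAP's Lugano-only endpoint (the protocol has "Response assessments according to the Lugano Classification and/or mSWAT").
- **Lost power from the 2-to-4 continuation rule.** Five or more responses in 11 already satisfy 4 of 18, and only 0 or 1 closes enrolment, so the stated 80% holds.

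**Conclusion.** The concern holds as a changed and undeclared inferential target. The protocol's formal test concerns 18 unselected subjects at one-sided 0.087. The SAP's concerns the pooled FAS, planned at 65, at two-sided 0.05 with a one-directional alternative. No stated operating characteristic is materially wrong, and the SAP may set the analysis, but a change of this kind belongs in Section 14.

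On the assumed mix of 37 AITL/TFH and 27 other subjects, AITL activity alone produces a pooled rejection with probability about 0.76 to above 0.99 with the gates ignored, and about 0.14 to 0.22 jointly with the 4/18 gate. Enrolment has moved past Stage 2, so the ungated range is closer to the question of how to read the final p-value. These figures rest on the assumed evaluable numbers, AITL ORRs of 30% to 50%, and 10% in everyone else. A pooled rejection would support activity somewhere in the enrolled mix, not in unselected PTCL.

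**What to change.** 1. In SAP Sections 4 and 8.1, keep the formal test of 10% in the initial 18 subjects under the protocol's rule (at least 4 of 18, one-sided 0.087; alpha 0.0875 and power 0.800 as reproduced above). Report the pooled FAS ORR with its interval beside the subtype ORRs already planned. Label any pooled p-value descriptive and not evidence of activity in unselected PTCL.
2. In SAP Section 14, list the change in test population, N, alpha and sidedness, and state whether the extension subjects enter the pooled test. In Section 8.1, make the alternative and the sidedness of the test agree.

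The cost is SAP wording, with no new data and no new analysis. The sponsor gives up a formal pooled p-value, which the protocol did not plan.

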5. ANALYSIS POPULATIONS

Full Analysis Set (FAS)

FAS will include the data on study participants who received at least one dose of tipifarnib and had at least one post-dose disease response assessment.

[REDACTED]

[REDACTED]

All Subjects as Treated (ASaT) Population

The ASaT population consists of all enrolled subjects who received at least one dose of tipifarnib and have at least one post-dose safety assessment (any laboratory, vital sign, or other safety assessment).

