6.4. Handling of Dropouts or Missing Data

The primary analysis will be based on the observed available data – no data imputations will be conducted. For the survival analysis, dropouts without confirming events will be treated as censored.

As part of the exploratory analysis, sensitivity analysis using appropriate data imputation models may be conducted. The impact of different imputation models will be assessed and compared to main analysis.

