7. SUMMARY OF STUDY POPULATION DATA

7.1. Subject Disposition

Subject disposition will be provided for all subjects screened. The disposition table will include the total number of subjects screened, total number of screen failures, and total number who received any study drug will be displayed. Among subjects who received any study drug, frequency and percentage of subjects who completed treatment, prematurely discontinued and reasons for premature discontinuation and reason for end of study will be tabulated. Subjects will be presented throughout by their genetic subtype: AITL, PTCL, CXCL12+, and an Other category, which includes one subject that is ALCL-ALK negative and one that is PTCL sub-type not otherwise specified in the protocol.

Detailed subject disposition information, subject eligibility, and analysis population assignment will be displayed in separate listings.

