7.3. Demographics and Baseline Characteristics

Descriptive statistics will be provided for subject demographics and baseline characteristics. The following summary tables will be provided:

- Demographics and baseline characteristics at screening to include age and sex.
- Ethnicity and race will be stated where allowed by local regulatory authorities. Measurements of height, weight, and ECOG performance status score will be summarized for the ASaT, FAS, [REDACTED] Populations.
- Medical and surgical history/physical findings will be coded using Medical Dictionary for Regulatory Activities (MedDRA) version 19.0 and summarized by system organ class (SOC)/preferred term (PT) for the ASaT population.
- Cancer history at screening will be summarized by diagnosis and stage for the ASaT population.
- Prior anti-cancer therapy, cancer surgery and radiation therapy will be summarized for the ASaT population and for the FAS population. For prior anti-cancer therapy, descriptive statistics on the number of regimens per subject and best overall response on last prior therapy will be presented.
- Last therapy progression free survival will be presented. Progression free survival on last prior therapy will be calculated as follows:

$([\text{Progression Date} - \text{Earliest Treatment Initiation Date of Most Recent Prior Cancer Therapy}] + 1)/30.4375$. If date of progression is not available for the last prior therapy, then the start date of Tipifarnib will be used to calculate PFS.

- Kaplan Meier curves will present a comparison PFS on last prior therapy for the ASaT population by cohort compared to PFS on tipifarnib using a Cox Proportional Hazards model.

The following listings will be provided:

- Subject demographics
- Baseline medical, surgical history/physical findings
- Biopsy sample at screening
- Buccal swab sample at screening
- Cancer history at screening

- Previous anti-cancer therapy
- Prior cancer surgery
- Prior radiation therapy
- Disease related symptom assessment at screening
- Prior stem cell transplants at screening
- ECOG performance status

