8.2. Secondary Efficacy Analysis

The secondary efficacy analysis will focus on DOR and PFS analysis in the study population (FAS analysis data set), as well as on subgroup analysis of ORR, PFS, and DOR in genetic sub-types (AITL, PTCL-NOS, CXCL12+, and Other).

The duration of the response will be calculated for subjects who achieve an objective response (either CR or PR, whichever comes first). For such subjects, the duration of the objective response is defined as the number of days from the start date of the objective response to the first date of either documented progressive disease or death. All efforts will be made to objectively define the endpoint by collecting the necessary data and reducing the likelihood of missing data. In the event of a maintained response, the DOR will be censored at the last evaluable non-PD assessment.

Disease progression will be determined by the investigator using the primary efficacy endpoint assessment. Progression free survival will be defined as the time (in months) from first dose (Cycle 1 Day 1) to the minimum date of progression or death, if death occurred within 126 days

³ Wilson, E. B. (1927). "Probable inference, the law of succession, and statistical inference". *Journal of the American Statistical Association*. 22 (158): 209–212.

⁴ Clopper, C.; Pearson, E. S. (1934). "The use of confidence or fiducial limits illustrated in the case of the binomial". *Biometrika*. 26 (4): 404–413.

of the last treatment or assessment. If the subject goes off study with no documentation of PD, the censoring date will be the date of the last evaluable assessment.

Sensitivity analyses may be conducted to explore the effect of different censoring on DOR and PFS.

The duration of the objective response and progression free survival will be analyzed using the Kaplan-Meier (KM) method. 95% CI for KM curve will be constructed using Greenwood's⁵ formula in the log-log scale.

The median DOR and PFS will be evaluated using the 50th percentile of KM distribution. 95% CIs for the median will be constructed based on a robust nonparametric method of Brookmeyer and Crowley⁶.

Summary tables and advanced data visualizations will be used for presenting KM plots, 95% CIs for probabilities of surviving X months, and a median survival estimate with its 95% CIs. The analysis will be conducted on FAS (primary) [REDACTED] populations.

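### The primary efficacy set omits dosed subjects with no post-dose response assessment, so its ORR is higher than the ORR over all dosed subjects, and PFS loses deaths that precede a first assessment

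*SAP*

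**What the plan says.** SAP Section 5 admits to the FAS only participants "who received at least one dose of tipifarnib and had at least one post-dose disease response assessment". Section 8.1 estimates the ORR "as a ratio of subjects with an objective response to the number of subjects (N) in the FAS data set". Section 6.4 says of the primary analysis that "no data imputations will be conducted", and adds only that, as exploratory work, "sensitivity analysis using appropriate data imputation models may be conducted".

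For PFS and DOR, Section 8.2 states "The analysis will be conducted on FAS (primary"; a redacted second population follows. PFS runs from first dose "to the minimum date of progression or death, if death occurred within 126 days" of the last treatment or assessment.

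Protocol 12.1.1 also names the FAS as the primary efficacy population. It excludes subjects who lack post-baseline endpoint data after at least one dose. Protocol 12.2.1 counts a death as a PFS event if it falls within 126 days of either the first administration or the last tumor assessment. It also allows censoring at the date of first administration.

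Two other SAP items bear on the point. Section 7.1 says "Detailed subject disposition information, subject eligibility, and analysis population assignment will be displayed in separate listings". Section 7.3 says "Kaplan Meier curves will present a comparison PFS on last prior therapy for the ASaT population by cohort compared to PFS on tipifarnib".

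**The concern.** The primary objective is to determine the ORR of treated subjects with relapsed or refractory PTCL. A subject who took the drug and was never assessed cannot be a documented responder. Leaving that subject out keeps the numerator and shrinks the denominator, so the reported rate describes assessed subjects and is higher than responders over all dosed.

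Entry to the set can also depend on outcome. The first scheduled assessment is about seven weeks after first dose, and a subject who dies before it with no other assessment never enters the FAS. For PFS this conflicts with the plan's own event rule: the protocol's clause on death within 126 days of first administration, and its first-dose censoring date, both provide for subjects with no post-baseline assessment. The SAP's entry rule removes these subjects before either provision can apply.

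At stake are the headline ORR and the PFS curve.

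**Working it through.** **1. The plan's own figures.** SAP Section 4 gives gates of at least 2/11 and at least 4/18, then a two-sided 0.05 normal-approximation test of 10% at N = 65.
- With z = (r/N − 0.10)/√(0.10 × 0.90/N), 11/65 gives z = 1.86 and 12/65 gives z = 2.27, so 12 responders are needed.
- Exact enumeration through both gates gives 0.797 at a true ORR of 30% (SAP: about 80%) and 0.992 at 50% (SAP: about 99%).
- At 10%, the chance of passing Stage 1 is 0.303 (SAP: 30%) and of passing Stage 2 is 0.087 (SAP: 8%).

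The design arithmetic holds, but it is stated in evaluable subjects.

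**2. ORR.** Let R be responders, T dosed, U dosed but never assessed, and d = U/T. Then FAS ORR = R/(T − U) = (R/T)/(1 − d).

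**3. Size.** The documents do not give d. SAP Section 4 assumes 65 evaluable and the cap is 70, but Protocol 12.4 uses evaluable to mean dosed, so the gap of 5 need not be unassessed subjects. As assumptions:

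| d | 1/(1 − d) | all-dosed 10% appears as | all-dosed 30% appears as |
|---|---|---|---|
| 5/70 = 7.1% | 1.077 | 10.8% | 32.3% |
| 10% | 1.11 | 11.1% | 33.3% |
| 20% | 1.25 | 12.5% | 37.5% |

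**4. Effect on the test.** SAP 8.1 ties the test to the interval method, which is Wilson when there are more than four responders.
- Protocol 5.2 reports 5 CR and 4 PR among all AITL subjects, so 9 responders.
- Protocol 12.4 and the Synopsis report 5 responses in the CXCL12+ cohort, 2 of them with AITL histology, so 3 non-AITL responders.
- The total is at least 9 + 3 = 12, before the subjects added by Amendment 7.
- 12/70: z = (0.1714 − 0.10)/0.0359 = 1.99, Wilson lower bound 10.09%. 12/65: lower bound 10.9%. Both reject.
- With 11 responders the sets could disagree: 11/63 has a lower bound of 10.04% and 11/70 of 9.0%. That would need at least 7 of 70 unassessed and only 11 responders, which is fewer than already reported.

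**5. PFS.** Cycle 2 Day 22 is day 28 + 22 = 50, with a window of day 45 to 55. Take 65 FAS subjects with exponential PFS and 5 unassessed, of whom k die early and the rest are censored at first dose. With f = k/(k + 65), the all-dosed median divided by the FAS median is ln((1 − f)/0.5)/ln 2:
- k = 1: 0.978
- k = 3: 0.935
- k = 5: 0.893

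DOR is unaffected, because it starts from a documented response.

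**6. Illustration from the interim report (Protocol 5.2).** Its analysis set has the same two conditions, a dose and a post-baseline assessment. Dividing the same responders by all enrolled gives:
- AITL cohort: 5/11 = 45.5% becomes 5/16 = 31.3%
- CXCL12+ cohort: 5/12 = 41.7% becomes 5/15 = 33.3%
- All AITL: 9/17 = 52.9% becomes 9/23 = 39.1%

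**The case against.** The strongest reply has five parts.

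- **The exclusion is pre-specified.** For ORR this is correct. The endpoint is response assessments, so Protocol 12.1.1 already excludes the same subjects, and a reader who infers that the SAP changed the ORR population would be wrong. The SAP is narrower only for PFS: endpoint data could include a death, a disease response assessment cannot, and SAP Section 14 does not list the difference.
- **The bias need not favour the drug.** This stands in part. An unassessed subject's response is missing, and counting it as non-response is a convention. The FAS rate cannot be lower than the rate under that convention, but it need not misstate the response probability if assessments are missing for unrelated reasons.
- **Few subjects may be affected.** This may be so. Protocol 10.1 accepts physical as well as radiological assessments, extra assessments are allowed, and an End of Treatment assessment is due after discontinuation without progression if none was done in the prior 8 weeks.
- **Other analyses may cover it.** SAP 8.1 plans an ORR table for the FAS and a redacted population, so a reader cannot conclude that no all-treated ORR is planned. The SAP 7.3 display may show PFS on tipifarnib in the ASaT population, and listings will show population assignment and deaths. None of these displaces the FAS as primary, and the imputation analyses are optional.
- **Changing the primary set now is itself data-aware.** This stands. The trial is open-label and results for 50 subjects have been reported, so any change must be labelled accordingly.

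**Conclusion.** The point holds as one about estimates. The primary ORR is the all-dosed ORR divided by (1 − d), and the FAS rule removes from PFS early deaths that the plan's own event definition would count. Under the assumed 5 unassessed of 70, 30% would be reported as 32.3%, and the all-dosed PFS median would be 89% to 98% of the FAS median for 5 down to 1 early deaths, on an exponential assumption.

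Two stronger readings are not supported. A reader might infer that the exclusion could turn a failed test against 10% into a success. With at least 12 responders already implied and a cap of 70, it cannot, unless a responder is later excluded or reclassified. This rests on the Wilson-based test that SAP 8.1 points to; an exact test with a 0.025 upper tail would need 13 at both N = 65 and N = 70. A reader might also take the interim shortfalls of 20% to 31% (3/15 and 5/16) as the final d. Some of those subjects may have been awaiting a scan, replaced, or removed for CXCL12 status, so the counts neither fix nor bound it.

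The change is worth making because it is cheap and the effect on the reported ORR is unquantified.

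**What to change.** In SAP Sections 5, 8.1 and 8.2:
- Define a set of all subjects with at least one dose. The ASaT set as written also requires a post-dose safety assessment, so it is close but not identical.
- Require ORR over this set, counting subjects with no post-dose response assessment as non-responders.
- Require PFS over the same set, counting deaths before any assessment under the existing 126-day rule and censoring other unassessed subjects at first dose, as Protocol 12.2.1 provides.
- Make this the primary analysis or, at minimum, a mandatory analysis reported beside the FAS result, with the number of subjects excluded from the FAS and the reasons.
- State how dosed CXCL12+ subjects later found to have a somatic variant are handled, since Protocol 12.4 lets them be left out of efficacy analyses. Including them in the all-dosed set and omitting them only from the CXCL12+ subgroup would keep the two rules consistent.
- Record the change in SAP Section 14 as made after interim results were known.

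The cost is SAP wording and one further set of ORR and PFS tables, with no new data. If anyone is unassessed, the all-dosed ORR may be lower than the FAS figure and PFS may be shorter. If nobody is, the results are unchanged.
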